6.0 SUBJECT POPULATION

6.1 Number of Subjects

Approximately, 40 subjects are planned to be randomized at a 1:1 ratio into two treatment arms (20 subjects in the VERU-111 treated group and 20 subjects in the Placebo treated group).

The subjects with documented evidence of COVID-19 infection (by standard diagnostic method) will be enrolled. Subjects will be at high risk for the development of ARDS.

6.2 Selection Criteria

6.2.1 Inclusion Criteria

Subjects accepted for this study must:

- 1. Provide informed consent
- 2. Be able to communicate effectively with the study personnel
- 3. Aged ≥ 18 years

- 4. Severe Acute Respiratory Syndrome Coronavirus (SARS-CoV-2) infection confirmed by polymerase chain reaction (PCR) test
- 5. Patients at high risk for ARDS, with known comorbidities for being at high risk, such as, Asthma (moderate to severe), Chronic Lung Disease, Diabetes, Chronic Kidney Disease being treated with dialysis, Severe Obesity (BMI ≥40), 65 years of age or older, primarily reside in a nursing home or long-term care facility, or immunocompromised.
- 6. Peripheral capillary oxygen saturation (SpO₂) ≤ 94% on room air at screening. If patient is on oxygen therapy at the time of presentation for screening and the SpO₂ levels were ≤94% prior to introduction to oxygen therapy with proper documentation example EMT notes or ER/ED notes, then the patient is considered to have met this inclusion criterion. If patient is on oxygen therapy at the time of presentation for screening and the SpO₂ levels prior to introduction to oxygen therapy are unknown, the patient may be considered to have met this inclusion criterion if oxygen therapy is removed and the SpO₂ levels fall to ≤94%, then the patient is considered to have met this inclusion criterion. However, removal of the oxygen therapy should only be done if it is considered medically reasonable.
- 7. Subjects must agree to use acceptable methods of contraception
 - If subject is female or the male subject's partner could become pregnant, use acceptable methods of contraception from the time of the first administration of study medication until 6 months following administration of the last dose of study medication. Acceptable methods of contraception are as follows: Condom with spermicidal foam/gel/film/cream/suppository [i.e., barrier method of contraception], surgical sterilization (vasectomy with documentation of azospermia) and a barrier method {condom used with spermicidal foam/gel/film/cream/suppository}, the female partner uses oral contraceptives (combination estrogen/progesterone pills), injectable progesterone or subdermal implants and a barrier method (condom used with spermicidal foam/gel/film/cream/suppository))
 - If female subject or the female partner of a male subject has undergone documented tubal ligation (female sterilization), a barrier method (condom used with spermicidal foam/gel/film/cream/suppository) should also be used
 - If female subject or the female partner of a male subject has undergone documented placement of an intrauterine device (IUD) or intrauterine system (IUS), a barrier method (condom with spermicidal foam/gel/film/cream/suppository) should also be used
- 8. Subject is willing to comply with the requirements of the protocol through the end of the study

6.2.2 Exclusion Criteria

Any of the following conditions are cause for exclusion from the study:

- 1. Known hypersensitivity or allergy to colchicine
- 2. Participation in any other clinical trial of an experimental treatment for COVID-19. Convalescent plasma and remdesivir are allowed in this study.

- 3. Concurrent treatment with other experimental agents with actual or possible direct acting antiviral activity against COVID-19 is prohibited < 24 hours prior to study drug dosing (except standard of care). Remdesivir and convalescent plasma are allowed in the study.
- Requiring ventilation + additional organ support pressors, RRT, ECMO (WHO Ordinal Scale for Clinical Improvement – Score of 7) and patients requiring ventilation with a WHO Ordinal Scale for Clinical Improvement – Score of 6 for >5 days at screening.
 - Patients on ventilation with a WHO Ordinal Scale for Clinical Improvement Score of 5 (non-invasive ventilation or high-flow oxygen) are allowed into the study.
 - Patients on ventilation with a WHO Ordinal Scale for Clinical Improvement Score of 6 (intubation and mechanical ventilation) for less than five (5) days are allowed into the study.
- 5. Alanine Aminotransferase (ALT) or aspartate aminotransferase (AST) >2 X upper limit of normal (ULN)
- 6. Total bilirubin > ULN
- 7. Creatinine clearance < 60 mL/min
- 8. Documented medical history of liver disease, including but not limited to, prior diagnosis of hepatitis of any etiology, cirrhosis, portal hypertension, or confirmed or suspected esophageal varices
- 9. Moderate to severe renal impairment
- 10. Hepatic impairment
- 11. History of hepatitis
- 12. Any comorbid disease or condition (medical or surgical) which might compromise the hematologic, cardiovascular, endocrine, pulmonary, renal, gastrointestinal, hepatic, or central nervous system; or other conditions that may interfere with the absorption, distribution, metabolism or excretion of study drug, or would place the subject at increased risk
- 13. Participants must agree to refrain from prolonged exposure to the sun or agree to use at least SPF 50 on all exposed skin and protective clothing during prolonged sun exposure throughout participation in this study and/or treatment with VERU-111.

7.0 STUDY MEDICATION

7.1 Enrollment and Blinding

The study will be a randomized, double-blind, placebo-controlled study. The study will be unblinded when the last patient has completed the Day 29 assessments.

An emergency code break will be available to the investigator / pharmacist / investigational drug storage manager. This code break option in IWRS may only be disclosed in emergency situations when the identity of the trial drug must be known to the investigator in order to provide appropriate medical treatment or if required to assure safety of trial participants. If the code break for a patient is opened, the sponsor and CRO will be informed immediately via IWRS notification. The reason for the IWRS unblinding of the subject must be documented on the appropriate eCRF page along with the date and the initials of the person who broke the code.

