5.2 Study Duration

The study will require that each subject in the VERU-111 treated groups receive 18 mg daily oral dose of VERU-111 or placebo for up to 21 days (Day 21) with final on study efficacy assessments done on Day 29 with safety assessments continuing to Day 60 of the study. The total duration of the study for a subject in the study from screening to follow-up visit (approximately Day 60 on study) will be approximately 62 days.

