8.7 Day 29 ± 3 days

The following assessments will be performed at approximately Day 29 (\pm 3 days):

- 1. Vital Signs (temperature/pulse/supine blood pressure)
- 2. SpO₂
- 3. Physical examination (including weight)
- 4. 12-lead ECG (single)
- 5. Chest X-ray or CT scan
- 6. Clinical Laboratory tests
 - a. Hematology (Appendix A)
 - b. Serum chemistry (Appendix A)
 - c. Urinalysis
- 7. Adverse events
- 8. Record the usage of any concomitant medications and ongoing treatments.
- 9. Assessment of primary and secondary endpoints
- 10. Pregnancy test

8.8 Follow up visits at Day 45 (± 3 days) and Day 60 (± 3 days) (can be conducted via phone/teleconference)

- 1. Adverse events
- 2. Assessment of primary and secondary endpoints (observational assessment)

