8.11.4 Initial Reports

SAEs will be collected from the time of first study drug administration through 60 days after first study drug administration. SAEs and events of clinical interest must be reported to the Sponsor (or designee) within 24 hours of the knowledge of the occurrence.

In the event an SAE is observed or reported, the SAE report will be completed as thoroughly as possible including all available details about the event and the signature of the Investigator. If the Investigator does not have all information about an SAE, the Investigator will not wait to receive additional information before notifying the Sponsor of the event and completing the form. The form will be updated when additional information is received.

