9.7.1 Data Safety Monitoring Board

A Data Safety Monitoring Board will review the unblinded safety data from this Phase 2 study, including all SAEs, every 2 weeks, or more often if the safety observations.

The recruitment of this Phase 2 study is expected to be completed within 4 weeks of first patient, first dose. Therefore, from first patient, first dose, to last patient, last dose is expected to be <50 days.

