#### **6.12.2** Secondary Endpoints

# 6.12.2.1 Change in mean WHO Ordinal Scale for Clinical Improvement at Day 15, Day 22 and Day 29

The mean change in WHO Ordinal Scale for Clinical Improvement from baseline to Day 15, Day 22 and Day 29 will be assessed.

Baseline for WHO Ordinal Scale is the last available record up to and including Day 1. If subject died or was discharged from the hospital prior to Day 15, 22 or 29 and WHO Ordinal Scale for Clinical Improvement is not collected or record is otherwise missing at those timepoints then the last available observation before or at the time of death/discharge will be carried forward.

Analysis will be performed using two different approaches, including the LOCF values and excluding LOCF values. Further, these analyses will be repeated using separate baseline definition. As the time of WHO Ordinal Scale is collected it cannot be definitely confirmed if Day 1 record was taken before or after start of study treatment. Sensitivity analysis will be performed using the WHO Ordinal Scale from Screening record.

Descriptive statistics (n, mean, standard deviation, median, minimum and maximum) will be summarized for absolute values and change from baseline by treatment group and visit.

Change from baseline will be analyzed using mixed model for repeated measures (MMRM) including treatment, visit and treatment-by-visit interaction as fixed effects, and study site, remdesivir use (No/Yes), dexamethasone use (No/Yes) and WHO Ordinal Scale for Clinical Improvement at baseline as covariates. The resulting F-tests will be based on Kenward-Roger's adjusted degrees of freedom. Subject effect will be assumed to be random and an unstructured covariance structure will be used for within subject variation. If this model does not converge then the following covariance matrices will be used in order until the model converges: Toeplitz, first-order autoregressive, and compound symmetry. Least squares means, standard errors, 95% confidence intervals and p-values for treatments and treatment differences at each visit (study days 15, 22, 29, 45 and 60) will be presented.

QMD Ref: Worldwide-TMP-ST-005-7.0 Effective: 12Aug2019 Governing QMD: Worldwide-SOP-ST-0		
Confidentiality Statement		
This document is the property of Worldwide Clinical Trials Inc. and may not be duplicated, copied, altered or removed from company without		

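### Protocol 7.1 unblinds the study at the last Day 29 visit without saying who stays blinded, so some Day 45 and Day 60 data that enter a planned treatment comparison may be collected with allocation known

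*Protocol*

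**What the plan says.** Protocol 7.1 calls the study double-blind and sets one unblinding point: "The study will be unblinded when the last patient has completed the Day 29 assessments". It does not say who receives the allocation, and no other section keeps sites, subjects or assessors blinded afterwards.

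Data collection runs on past that point:

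- Protocol 5.2 describes the follow-up as "with final on study efficacy assessments done on Day 29 with safety assessments continuing to Day 60 of the study".
- Protocol 8.8 schedules "Follow up visits at Day 45 (± 3 days) and Day 60 (± 3 days) (can be conducted via phone/teleconference"). Its two items are adverse events and "Assessment of primary and secondary endpoints (observational assessment"). The schedule in Appendix B agrees.
- Protocol 8.11.4: "SAEs will be collected from the time of first study drug administration through 60 days after first study drug administration". Under 8.11.2 the investigator judges causality.

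The late scores are also analysed. SAP 6.12.2.1 is headed for Days 15, 22 and 29, but its repeated-measures model ends with least squares means, confidence intervals and p-values, and "treatment differences at each visit (study days 15, 22, 29, 45 and 60) will be presented".

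On timing, Protocol 9.7.1 says: "The recruitment of this Phase 2 study is expected to be completed within 4 weeks of first patient, first dose". The synopsis and Protocol 9.5 later describe enrolment as unexpectedly slow and give no duration.

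**The concern.** Once the last subject reaches Day 29, every subject enrolled shortly before still has one or two contacts to come. If the people making or answering those contacts know the allocation, the WHO score is open to assessment bias. The part most exposed is the bottom of the scale, where scores 1 and 2 differ only in whether activities are limited. For a discharged subject that may be judged over the telephone. Causality calls on late adverse events are open to the same influence.

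Two planned results could be touched. One is the Day 45 and Day 60 treatment difference in the WHO score, which carries a p-value. The other is the set of Day 15, 22 and 29 estimates for the named secondary endpoints, because all five visits sit in one model and late scores can shift the earlier estimates slightly.

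**Working it through.** **The plan's own timing figures.** Protocol 9.7.1 expects fewer than 50 days from first dose in the first patient to last dose in the last. Four weeks of recruitment plus 20 or 21 days of dosing gives 28 + 20 = 48 or 28 + 21 = 49, so the figure reproduces. The 62-day duration per subject also reproduces: 2 screening days + 60. The documents state no share of contacts falling after unblinding.

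**Who has a contact after unblinding.** A subject enrolled e days before the last subject is on study Day 29 + e when the last subject reaches Day 29. A contact due on Day d is still to come if 29 + e < d, that is, if e < d − 29:

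- Day 45: e < 16
- Day 60: e < 31

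With 28 days between first and last enrolment, the first subject is on Day 29 + 28 = 57 at unblinding, so even that subject's Day 60 contact lies ahead.

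**Share of subjects.** Assume uniform accrual over R days. The share is min(1, (d − 29)/R).

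| Accrual | Source | Day 60: min(1, 31/R) | Day 45: min(1, 16/R) |
|---|---|---|---|
| 4 weeks, R = 28 | Protocol 9.7.1 forecast | 31/28, capped at 100% | 16/28 = 57% |
| 12 weeks, R = 84 | assumed | 31/84 = 37% | 16/84 = 19% |
| 20 weeks, R = 140 | assumed | 31/140 = 22% | 16/140 = 11% |
| 26 weeks, R = 182 | assumed | 31/182 = 17% | 16/182 = 9% |

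For 40 evenly spaced subjects this is 40 (Day 60) and 23 (Day 45) at 28 days. At 182 days it is about 7 (40 × 0.170 = 6.8) and between 3 and 4 (40 × 0.088 = 3.5). Subjects who have died or withdrawn have no contact, so these are upper counts for each R.

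**Visit windows.** The Day 29, 45 and 60 visits each carry ±3 days. The extremes pair unblinding on Day 32 with an early contact, and unblinding on Day 26 with a late one.

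- R = 28, Day 60: (57 − 32)/28 = 89% up to the cap of 100%
- R = 28, Day 45: (42 − 32)/28 = 36% to (48 − 26)/28 = 79%
- R = 182, Day 60: 25/182 = 14% to 37/182 = 20%
- R = 182, Day 45: 10/182 = 5% to 22/182 = 12%

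**What the late safety data feed.** SAP 6.15.1 counts an event as treatment-emergent only if onset or worsening comes before last dose + 7 days. Dosing ends by Day 21, so the window closes before Day 21 + 7 = 28. The by-arm adverse event tables in SAP 6.15.1 and section 11 are all treatment-emergent tables. An event starting near Day 45 or 60 reaches only the listing of all adverse events and, if fatal, the listing of deaths.

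**The case against.** The strongest reply is that 7.1 does not say sites or subjects are told. The SAP's list of outputs marks some tables for a preliminary analysis, which is compatible with unblinding an analysis team only. On that view this is a gap in wording, and unblinding at the primary time point of a 40-subject proof-of-concept study is an ordinary choice. Days 45 and 60 are not named endpoints, Protocol 8.8 calls those assessments observational, and SAP 6.12.4 treats all secondary and supportive analyses as descriptive. Much of the WHO scale (hospitalisation, ventilation, death) leaves little to judgement, and contacts may be by telephone but need not be.

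Most of this stands, and it limits the point. It does not remove it. The rule as written applies to the whole study, the table marking does not establish a firewall, and the SAP still attaches p-values to the late visits.

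A reader might infer more than the documents support:

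- **That allocation is in fact known at the late contacts.** The recipients are not named, so the data are only potentially unblinded.
- **That 17% to 100% of subjects are affected at both visits.** That range holds for Day 60; on the same assumptions Day 45 is 9% to 57%. Only the 4-week end comes from the documents, and the protocol itself reports slower recruitment.
- **That the by-arm safety comparison is exposed.** The treatment-emergent window keeps late-onset events out of it.
- **That affected subjects being the later-enrolled ones biases the arms.** Under 1:1 randomisation, enrolment date alone does not.

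**Conclusion.** The point holds with limited impact, and the sponsor should act on it. Protocol 7.1 opens the blind while assessments that feed a planned treatment comparison are still being made, and it keeps no one blinded.

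Under uniform accrual, the potentially affected share is about 100% of subjects at Day 60 and 57% at Day 45 for a 4-week recruitment, before visit windows. It falls to 17% and 9% for an assumed 26 weeks. Actual accrual is not stated, so the true share cannot be fixed from the documents. It is never zero by design, because the last subject's Day 45 and Day 60 contacts always follow unblinding.

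A reader might conclude that the primary result is compromised. It is not by this route: Day 29 status is collected before the unblinding in 7.1. What remains exposed is the late WHO comparison, slightly the Day 15 to 29 estimates fitted in the same model, and the causality calls in the late adverse event listings.

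The planned interim analysis adds nothing here, because SAP section 7 says it will not be performed. The synopsis does, however, plan a between-arm evaluation after the last Day 22 visit, which precedes the unblinding in 7.1. Those two passages should be reconciled.

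**What to change.** **Preferred.** Amend Protocol 7.1 so that investigators, site staff, subjects and anyone assessing adverse events or causality, including the medical monitor, stay blinded until the last Day 60 contact is complete. After the last Day 29 visit, unblind only a named, firewalled analysis team, working on a locked Day 29 extract. The same amendment should say who, if anyone, sees allocation for the Day 22 evaluation in the synopsis.

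**Otherwise.** Take Days 45 and 60 out of the SAP 6.12.2.1 model and drop their p-values. Report those visits descriptively and label Day 30 to 60 data as potentially unblinded.

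**Cost.** The preferred route needs a documented access restriction and a separate Day 29 data lock. The firewall has to run inside both organisations: under Protocol 10.1 the CRO handles data management and statistics while the sponsor handles clinical monitoring, and the medical monitor sits with the CRO. The Day 29 analysis need not wait for Day 60. Sites learn the allocation about 60 − 29 = 31 days later. The alternative needs only a SAP change, but gives up inference at Days 45 and 60.

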7.2 Drug Supply

7.2.1 VERU-111 Capsules

VERU-111 18 mg dose will be supplied as capsules containing 18 mg of VERU-111. Capsules will be supplied in bottles containing 21 capsules in each bottle. Patients will take one VERU-111 capsule per day.

The VERU-111 capsules should be stored at controlled room temperature, 20°C to 25°C (68°F to 77°F) with excursions permitted between 15°C to 30°C (59°F to 86°F).

7.2.2 Placebo Control

Placebo capsules contain zero (0) mg VERU-111 drug substance will be supplied in bottles containing 21 capsules each. The placebo capsules will contain only anhydrous lactose, USP. These capsules are identically appearing to the VERU-111 capsules. Patients will take one Placebo capsule per day.

The Placebo capsules should be stored at controlled room temperature, 20°C to 25°C (68°F to 77°F) with excursions permitted between 15°C to 30°C (59°F to 86°F).

7.2.3 Drug Accountability

Subjects should not take a replacement dose if a dose is missed. Study medication should not be taken more than once a day.

The pharmacists or other site personnel as delegated by the Investigator are responsible for accountability of all used and unused study drug supplies. A study drug dosing log should be kept current and should contain the dates and times drug dosing the subject, the subject's identification (i.e., subject number), the initials of the dispensing persons. Veru Inc., shall be immediately notified of any unexpected occurrences during the dispensing or dosing of study drug.

7.3 Drug Administration

Study drug should be taken daily at approximately the same time every day with approximately 240 mL (a full glass) of non-alcoholic liquid (drink). Dosing should occur within 30 minutes to 1 hour prior to the start of the morning meal. Subjects will take the entire daily dose at once. In subjects with a nasogastric feeding tube, the contents of the capsules may be emptied into the tube and appropriately flushed through the tube.

8.0 STUDY PROCEDURES

8.1 Screening

Potential subjects will be screened for this study in the 2 days prior to enrollment. The following activities will be conducted at screening:

- 1. Signed informed consent and HIPAA form will be obtained prior to any study-specific procedures and a copy of the signed consent form will be given to the subject.
- 2. Assess subject eligibility for inclusion into this study based on protocol inclusion/exclusion criteria.
- 3. Medical history will be obtained, including diagnosis of COVID-19 infection (date of diagnosis), details and dates of treatments received, documentation of symptoms related to COVID-19 infection.
- 4. The use of any medications will be recorded. This will include medications currently being taken and those taken since COVID-19 symptoms started. Over-the-counter (OTC) medications as well as medications taken on an as-needed basis (PRN) should be recorded.
- 5. Pregnancy test (female subjects only)
- 6. Vital signs (temperature/pulse/supine, if possible, blood pressure)
- 7. SpO₂
- 8. Physical examination including height and weight
- 9. Electrocardiogram- 12 lead (single)
- 10. Clinical Laboratory Tests
 - Hematology (Appendix A)
 - Serum chemistry (Appendix A)
 - Urinalysis

8.2 Enrollment

Enrollment should be done after the subject has completed the screening assessments and after it has been determined that the subject meets all the inclusion and exclusion criteria.

Subject will be randomized into one of two treatment groups.

8.3 Day 1

The Day 1 visit assessments will serve as the baseline assessments.

- 1. The medical history should be reviewed and updated to include any changes occurring since the screening visit. This will include the following:
 - a. Number of days from onset of COVID-19 symptoms to Day 1

- b. Specific reason for hospitalization
- 2. Assessment of eligibility
- 3. Vital signs (temperature/pulse/supine, if possible, blood pressure)
- 4. SpO_2
- 5. Physical examination (including weight)
- 6. Chest X-ray or Computed Tomography (CT) scan
- 7. Clinical Laboratory Tests
 - a. Hematology (Appendix A)
 - b. Serum chemistry (Appendix A)
 - c. Urinalysis
- 8. Record the usage of any concomitant medications and ongoing treatments.
- 9. Adverse events (ongoing on Day 1)
- 10. First dose of study drug
- 11. Temperature and SpO₂ every 12 hours after dosing

8.4 Day 2 through Day 21

The following assessments will be conducted on each of Day 2 to Day 21

- 1. Temperature and SpO₂ every 12 hours
- 2. Vital signs (temperature/pulse/supine, if possible, blood pressure)
- 3. Record the usage of any concomitant medications and ongoing treatments. This should include the following:
 - a. Documentation of the standard of care
 - b. The clinical rationale for initiation of mechanical ventilation, if necessary
 - c. Documentation of supportive measures for ARDS (e.g., proning, paralytics, etc.)
 - d. Care decisions that are based on limitations of resources at the clinical site
- 4. Adverse events
- 5. Dose study drug
- 6. At the time of discharge from the hospital, patients should be advised to use refrain from prolonged exposure to the sun or use at least SPF 50 on all exposed skin and protective clothing during prolonged sun exposure until the Day 60 adverse event assessment.

8.5 Day 3, Day 9, and Day 15

The following additional assessment will be conducted on Days 3, Day 9 and 15:

- 1. Serum Chemistry (Appendix A)
- 2. Hematology (Appendix A)
- 3. Assessment of primary and secondary endpoints (Day 15 only)
- 4. Physical examination (including weight) (Day 15 only)
- 5. 12 lead ECG (single) (Day 15 only)
- 6. Pregnancy test (Day 15 only)

 Plasma samples for pharmacokinetic assessment will be taken at baseline (prior to dosing on Day 15) and at 4 hours (±2 hours), 12 hours (±2 hours) after dosing on Day 15, and at 24 hours (±2 hours) after dosing on Day 15 (prior to dosing on Day 16). (Day 15 only)

8.6 Day 22 ± 3 days (these assessments will also be done at Early Termination or Discontinuation from the study)

The following assessments will be performed on Day 22 (\pm 3 days):

- 1. Vital Signs (temperature/pulse/supine blood pressure)
- 2. SpO₂
- 3. Physical examination (including weight)
- 4. 12-lead ECG (single)
- 5. Chest X-ray or CT scan
- 6. Clinical Laboratory tests
 - a. Hematology (Appendix A)
 - b. Serum chemistry (Appendix A)
 - c. Urinalysis
- 7. Adverse events
- 8. Record the usage of any concomitant medications and ongoing treatments.
- 9. Assessment of primary and secondary endpoints

